11.4. Patient disposition and Baseline tables

The following numbers will be presented, grouped by cohort and overall:

- Number of patients Screened;
- Number of patients Screening Failures;
- Number of patients in DD population;
- Number of patients in Safety population;
- Number of patients in Efficacy population;
- Number of patients who discontinued and reason for discontinuation.

The following baseline characteristics will be summarised by descriptive statistics computed on the Safety population:

- Demographics characteristics;
- Medical History and Concurrent Medical Conditions;
- Acute Myeloid Leukemia specific Medical History;
- Mutation status;
- Prior and Concomitant medications;
- Prior and Concomitant procedures.

11.5. Safety analysis

Safety and tolerability assessments will be evaluated on the safety population by means of descriptive statistics. Summary statistics (counts / (%) | number of events) will report the incidence of AEs using combinations of these variables for the descriptive statistics stratification: CTCAE toxicity grade, relationship with study drug, seriousness, System Organ Class or Body System, Preferred Term.

AEs summary tables will be created by Cohort (dose level) and Overall.

Counts and percentages will be produced for the results of the ECG, laboratory values (clinical chemistry, haematology, coagulation, bone marrow and urinalysis), vital signs, physical examination, classified as Normal/Abnormal NCS/Abnormal CS by Cohort (dose level) and Overall, stratified by Visit and timepoint – if applicable.

For ECG and hematology, clinical chemistry, coagulation and bone marrow laboratory data, the change from baseline will be summarized for each post baseline visit with descriptive statistics by cohort. For hematology and clinical chemistry laboratory parameters shift tables will be presented with the counts of individual shifts from each of the reference range categories from baseline to the worst post-baseline value by laboratory parameter by cohort and dose level.

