### **Inclusion/Exclusion Criteria:**

#### ***Inclusion Criteria***

Patients are eligible to be included in study if they meet all of the following criteria:

1. Patient with diagnosis of AML (i.e.  $\geq 20\%$  blasts in bone marrow or peripheral blood) harboring IDH1 or IDH2 mutation (as per local assessment).
2. Provide written informed consent prior to Screening.
3. Male or female patients, age  $\geq 18$  years old.
4. Patient has no standard therapeutic options available (including IDH inhibitors where approved) and has:
  - a) Relapsed AML unsuitable for intensive chemotherapy;
  - b) Primary refractory AML unsuitable for intensive chemotherapy;

**Clarification note:** Patients naïve to IDH inhibitor are eligible ONLY if no IDH inhibitors are approved/available in the country/site where they are enrolled.

5. ECOG Performance Status 0, 1 or 2.
6. Adequate organ function at Screening, including:
  - a) Aspartate aminotransferase (AST) and alanine aminotransferase (ALT)  $\leq 2.5 \times$  the upper limit of normal (ULN);
  - b) Total bilirubin  $\leq 2 \times$  ULN;
  - c) Creatinine clearance  $\geq 40$  mL/min (Cockcroft-Gault formula) (see [Appendix B](#));
  - d) Left ventricular ejection fracture (LVEF)  $\geq 40\%$  as per local assessment practice.
7. A female of childbearing potential, defined as any female who has experienced menarche and who has not undergone successful surgical sterilization or is not postmenopausal (i.e. has serum follicle stimulating hormone level  $\geq 30$  IU/L in the absence of hormone replacement therapy, or complete absence of menses for at least 12 consecutive months which is not due to medication), must have a negative pregnancy test within 7 days prior to receiving study drug.
8. Sexually active male or female patients of childbearing potential are eligible providing that:

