## **Study Assessments:**

### ***Safety***

Adverse events, clinical chemistry, hematological, coagulation, lipid profile and urinalysis parameters will be assessed. All clinical AEs and laboratory abnormalities will be graded according to NCI CTCAE V4.03. DLT, SAEs and AEs leading to treatment discontinuations will be determined.

Patients will also undergo regular physical examination, vital sign, ECG and urinalysis assessments.

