5.4. Study Endpoints

5.4.1. Primary endpoints

Study Part 1:

- DLT evaluation at the end of one treatment cycle for each dose level.

Study Part 2:

- The number and frequency of AE, safety laboratory, vital signs and ECG assessments.

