6.3.3. Classification criteria

Adverse Events are graded for severity using the classifications of Common Terminology Criteria for Adverse Events (CTCAE) Version 4.03 (June 14, 2010). Further details about NCI CTCAE classification are specified in protocol version 12.0, section 7 and appendix C.

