For this study, the following events will be considered to be expected events in this population and during leukemia therapy (e.g. myelosuppression and events secondary to disease) and should not be reported to the Sponsor as serious events unless the Investigator considers any of these events to be clinically concerning and of unusual manifestation with regard to severity, duration, frequency, outcome or other characteristics of the event. It is important to note that these events (with the exception of progression of AML, consider unrelated to study drug), still need to be captured as AEs on the AE eCRF and will be reviewed by the DMC in aggregate with all cumulative safety data.

Expected events during leukemia therapy are:

- Myelosuppression due to disease or leukemia therapy:
 - Febrile or infection episodes.
 - Epistaxis or bleeding except for catastrophic CNS or pulmonary hemorrhage.
 - Anemia, neutropenia, lymphopenia, thrombocytopenia, leukopenia, leukocytosis.
- Events due to underlying disease:
 - symptoms associated with anemia:
 - Fatigue.
 - Weakness.
 - Shortness of breath.
 - Electrolyte abnormalities (sodium, potassium, bicarbonate, CO₂, magnesium).
 - Chemistry abnormalities (LDH, phosphorus, calcium, BUN, protein, albumin, uric acid, alkaline phosphatase, glucose).
 - Coagulation abnormalities.
 - Disease specific therapy (induction, maintenance, salvage, or stem cell therapy).
 - Alopecia.
 - Bone, joint, or muscle pain.
 - Liver function test abnormalities associated with infection or disease progression.
 - Disease progression.
- General therapy events:
 - Events attributed to the use, placement and/or insertion of catheters.
 - Renal failure associated with tumor lysis syndrome or antibiotic/antifungal therapy.
 - Rash due to antibiotic use.
- Hospitalization for the management of any of the above expected events.

Abnormal hematologic or clinical chemistry values, not considered to be clinically significant, will not be recorded on the adverse event eCRF, although all values will be recorded on the hematology and clinical chemistry laboratory eCRFs.

Causality Assessment of Adverse Events

All AEs (including SAEs) will be assessed for the relationship of the AE to the study drug using the following standard definitions:

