 Table 2.3.4: Serious Adverse Events leading to Drug Interruption by System Organ Class and Preferred Term
 Table 2.3.5: Serious Adverse Events leading to Drug Reduction by System Organ Class and Preferred Term
 Table 2.4.1: Serious and Related Adverse Events by System Organ Class and Preferred Term
 Table 2.4.2: Serious and Related Adverse Events by Grade, System Organ Class and Preferred Term
 Table 2.4.3: Serious and Related Adverse Events leading to Drug Withdrawn by System Organ Class and Preferred Term
 Table 2.4.4: Serious and Related Adverse Events leading to Drug Interruption by System Organ Class and Preferred Term
 Table 2.4.5: Serious and Related Adverse Events leading to Drug Reduction by System Organ Class and Preferred Term
 Table 2.5.1: Dose Limiting Toxicity by System Organ Class and Preferred Term
 Table 2.5.2: Adverse Events leading to Death by System Organ Class and Preferred Term
 Table 2.5.3: Related Adverse Events leading to Death by System Organ Class and Preferred Term
 Table 2.6: Overall summary of Haematology Laboratory Parameters by Visit
 Table 2.6.1: Change vs Baseline of Haematology Laboratory Parameters by Visit
 Table 2.6.2: Shift Table for Haematology Laboratory Parameters
 Table 2.7: Overall summary of Clinical Chemistry Laboratory Parameters by Visit
 Table 2.7.1: Change vs Baseline of Clinical Chemistry Laboratory Parameters by Visit
 Table 2.7.2: Shift Table for Clinical Chemistry Laboratory Parameters
 Table 2.8: Overall summary of Coagulation Laboratory Parameters by Visit
 Table 2.8.1: Change vs Baseline of Coagulation Laboratory Parameters by Visit
 Table 2.9: Overall summary of Lipid Panel Parameters by Visit
 Table 2.9.1: Change vs Baseline of Lipid Panel Parameters by Visit
 Table 2.10: Overall summary of Bone Marrow Laboratory Parameters by Visit
 Table 2.11.1: Change vs Baseline of Bone Marrow Laboratory Parameters by Visit
 Table 2.12: Overall summary of Urinalysis Laboratory Parameters by Visit (Categorical Variables)
 Table 2.12.1: Overall summary of Urinalysis Laboratory Parameters by Visit (Continuous Variables)
 Table 2.13: Overall summary of Echocardiogram by Visit
 Table 2.14: Overall summary of ECG by Visit
 Table 2.14.1: Change vs Baseline of ECG by Visit
 Table 2.15: Overall summary of ECOG Performance Status by Visit
 Table 2.16: Overall summary of Physical Examination Parameters by Visit
 Table 2.17: Overall summary of Vital Signs by Visit

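### The laboratory shift tables count reference-range categories, so no planned table counts patients by CTCAE grade of laboratory abnormality

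*SAP*

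**What the plan says.** The protocol synopsis, under Study Assessments (Safety), states: "All clinical AEs and laboratory abnormalities will be graded according to NCI CTCAE V4.03". The statement covers laboratory abnormalities as well as clinical events.

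The SAP uses the scale more narrowly. Section 6.3.3 reads "Adverse Events are graded for severity using the classifications of Common Terminology Criteria for Adverse Events (CTCAE) Version 4.03", and no section derives a grade from a laboratory value. For hematology and clinical chemistry, section 11.5 plans shift tables by cohort and dose level that give "counts of individual shifts from each of the reference range categories from baseline to the worst post-baseline value". In the index (section 13.2.1) these are "Table 2.6.2: Shift Table for Haematology Laboratory Parameters" and its clinical chemistry counterpart, Table 2.7.2. The index has no table of laboratory values by grade.

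Laboratory data carry weight in this study. The Part 2 primary endpoint in SAP section 5.4.1 is "The number and frequency of AE, safety laboratory, vital signs and ECG assessments".

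The adverse event tables by grade have a limit, set in SAP section 7.2.2 and in protocol section 7.6.1: "Abnormal hematologic or clinical chemistry values, not considered to be clinically significant, will not be recorded on the adverse event eCRF".

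**The concern.** A table of range categories records whether a value lies outside the normal range, not how far outside. Two kinds of patient are then poorly described. A patient already out of range at baseline who worsens in the same direction stays in the same category. A patient who starts in range and leaves it is counted the same way whether the abnormality is slight or severe.

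This trial makes its own safety decisions by grade. The dose-limiting toxicity criteria (protocol section 4.3) refer to grades of transaminase rise and electrolyte imbalance, and Table 10 of the protocol modifies dose by grade. Protocol section 1.5 names severe hepatotoxicity as a potential risk and reports hypophosphatemia at 25, 50, 75 and 150 mg. A reader of the study report would want to know how many patients reached each laboratory grade and from what starting grade. No planned table says so.

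**Working it through.** The plan gives no figure to reproduce, so the check sets the passages side by side and then looks at how the categories behave.

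**Can patients enter out of range?** Yes. Inclusion criterion 6 allows AST and ALT up to 2.5 times the upper limit of normal (ULN) and total bilirubin up to 2 times. Its organ-function list has no minimum for neutrophils, platelets or hemoglobin, and no limit on phosphate.

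**What does the shift table show?** The SAP does not define its categories. Low/normal/high is the natural reading.
- ALT from 2.4 to 12 times ULN: 12 / 2.4 = 5-fold rise. Counted as high to high, so no shift.
- ALT from 0.9 to 1.1 times ULN: 1.1 / 0.9 = 1.2-fold rise. Counted as normal to high, so a shift.

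The smaller change is visible and the larger is not. Only same-direction worsening is hidden; a move from low to high, or the reverse, would show.

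**How many patients?** The documents give no baseline distribution, so what follows is an assumption. Let *q* be the share of patients already out of range in the direction of worsening, let severe worsening be independent of baseline category, and let *N* patients worsen severely. The number shown as no shift is *N* × *q*. Taking *N* = 20, the planned size of the IDH-mutant cohort, as the extreme case in which all worsen:
- *q* = 25%: 20 × 0.25 = 5
- *q* = 50%: 20 × 0.50 = 10
- *q* = 90%: 20 × 0.90 = 18

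**How far would grading help?** A share *r* (no larger than *q*) may already be at the most severe grade at baseline. These patients show no shift under either method. Grading can therefore recover at most *N* × (*q* − *r*). With *q* = 90% and *r* = 50%, that is 20 × 0.40 = 8 of the 18. A smaller worsening that stays within one grade is also not shown.

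**Do other outputs supply the count?**
- Adverse event tables by grade: only for findings reported as adverse events.
- Normal / abnormal not clinically significant / abnormal clinically significant counts (SAP section 11.5): by visit and ungraded.
- Change from baseline: group statistics by visit. SAP section 11.2 includes the minimum and maximum, which reveal an extreme but not how many patients reached each grade.
- Figures 11 to 20: these cover ALT, AST, bilirubin and blood counts, but not phosphate.
- Listings 4.12 and 4.13: raw values, not a summary.

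None counts patients by laboratory grade.

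**The case against.** The strongest reply is that this is a choice of display in a descriptive study, and that severe changes will be seen elsewhere. Much of that stands.

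- **No specified analysis is breached.** A reader might infer from the synopsis that the SAP departs from a planned analysis. It does not. Protocol section 8.8 asks only that laboratory data be listed by cohort, dose and time-point, and the SAP already goes further. The synopsis speaks of grading, not of tabulation.
- **Severe hepatotoxicity would not go unseen.** Protocol section 7.2 counts clinically significant laboratory values and shifts from baseline as adverse events. A very large ALT rise is unlikely to be judged otherwise, given the named risk and the liver-function requirement for re-treatment in section 4.4. It should appear among the grade 3 or higher adverse events in Table 2.1.2.2 and Listing 4.11.1. Events exempt from serious-event reporting must still be recorded as adverse events. Listings are also readable at this size: protocol section 1.4 reports 48 patients dosed, with about 20 more planned.
- **Patients with raised baseline values are not shown to be at greater risk.** A reader might infer that the table fails those most exposed to liver toxicity. No passage says that raised entry transaminases increase the risk. They are only the patients in whom worsening is least visible in this table.
- **Grading has a ceiling.** Patients who enter with the most severe cytopenia gain nothing from it.

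The reply does not supply the missing count. The adverse event route depends on the investigator's judgment of clinical significance. The other outputs show extremes or raw values, not patients by grade.

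**Conclusion.** The point holds as a modest one. The protocol says laboratory abnormalities will be graded, while the SAP's shift tables use ungraded categories and no other planned table fills the gap. No data are lost, since all values are recorded on the laboratory eCRFs, and no primary result is biased. What is missing is a per-patient count by grade. It matters mainly for values judged not clinically significant, for blood counts and for phosphate.

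The size cannot be fixed from the documents. It depends on the share of patients out of range at baseline, for which the range above is illustrative only, and on low/normal/high being the intended categories. If the clinical-significance classes were meant instead, a move from not significant to significant would show, but worsening within the significant class would not.

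**What to change.** In SAP section 11.5 and the table index:

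- Derive CTCAE v4.03 grades for hematology and chemistry parameters that can be graded from the numerical value, including ALT, AST, bilirubin and phosphate.
- Where a parameter can be abnormal in both directions, grade high and low separately. The SAP does not at present say which direction is worst for such parameters.
- Present baseline grade against worst post-baseline grade in Tables 2.6.2 and 2.7.2, by cohort and dose level.
- Keep reference-range shifts for parameters without a CTCAE grade, and define the categories.

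The cost is modest programming to add grades to the laboratory analysis dataset. The values are already on the eCRF, and protocol section 5.3.6 provides for collecting each site's reference ranges. No new data, visits or patients are needed.

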11.5.1. Safety assessments

Safety and tolerability endpoints will be derived from the following measurements/evaluations:

- Incidence, severity (CTCAE grade), seriousness, and treatment related causality of AEs;
- Physical examination;
- Vital signs;
- Safety laboratory tests (Clinical Chemistry, Hematology, Coagulation, Lipid Profile and Urinalysis);
- 12-lead-ECG.

11.5.2. Adverse Events

All identified AEs are recorded and described on the appropriate AE page of the eCRF, except for those events occurring prior to the first SEL24/MEN1703 intake, which are recorded on the Medical History eCRF page. All Adverse Events recorded in the eCRF will be listed. All AEs summaries will be based on the safety population.

The following information will be reported for all AEs listings: cohort and dose, patient ID, case ID, date of onset and resolution, duration in days, severity (grade) and seriousness of the event, assessment whether the event was serious or non-serious, relationship to IMP, and action taken regarding the IMP. In the listings, all AEs and their eventual follow-up will be reported. The Sponsor assessment for seriousness and causality will also be reported except for patients enrolled under Selvita sponsorship.

AE attributes that will be summarized into a new binary variable

- **Relationship to study drug.** If the AE is judged as *Definitely Related*, *Probably Related* or *Possibly Related* then the AE will be judged as Related to the study drug. If the relationship assessment is missing, the AE will be considered as related.
- **Seriousness of the AE.** If the AE is judged as 'Serious' or 'Exception to SAE reporting', then the AE will be judged as 'Serious'.

The number and percentage of patients experiencing one or more AEs will be summarized in the safety tables by cohort, dose level, relationship to study drug, and seriousness.

An overview of AEs will be provided with the number and percentage of patients reporting an event by cohort, dose level and overall. The summaries will be presented for the following categories:

- Any Serious AE
- Any Related AE
- Any Serious and Related AE
- Any AE by Relationship, Outcome, Severity (Grade) or Action Taken

If a patient experienced an AE and some follow-up AEs with the same preferred term, the AE and its follow-up(s) will count as one. The relationship with IMP, the seriousness and the action taken will be used to make filters in the summary safety tables; all events will be included in the listings.

Additionally the different groups of AEs - expressed as number and percentage of patients with each AE - will be presented by cohort and overall, by dose level and overall, by System Organ Class and Preferred Term or by Grade, System Organ Class and Preferred Term.

11.5.3. Vital Signs

A summary table of Vital Signs (systolic and diastolic BP (Blood Pressure - mmHg), temperature, heart rate) by Visit will be provided in the TLFs.

11.5.4. Physical Examination

A summary table of Physical Examination parameters by Body System and Visit will be provided in the TLFs.

11.5.5. 12-ECG

A summary table of 12-Lead ECG interpretation by Visit will be provided in the TLFs. Similarly, changes from baseline for each post baseline visit will be summarised.

11.5.6. Safety laboratory tests

An overall summary table of clinical chemistry, haematology, coagulation, lipid profile, bone marrow and urinalysis parameters by Visit, cohort, dose and time-point will be provided in the TLFs. The change from baseline will be summarized for each post baseline visit with descriptive statistics by cohort.

12. Efficacy evaluations

Disease assessment will involve evaluation of leukemic blast proportion in the bone marrow.

Hematologic parameters from the routine local assessments including blast percentage (where applicable), absolute neutrophil count (ANC), platelet count, and other relevant parameters such as transfusion dependence will also contribute to this assessment. Evaluation of disease status will be performed at the time-points described in the Schedule of Study Assessment (Table 5). To note, disease assessment must be performed as soon as the peripheral lab results become consistent with an objective response. Disease assessment will also include an aliquot of bone marrow aspirate/biopsy that will be centrally stored for future analysis (e.g. minimal residual disease), if any.

In case bone marrow aspirate/biopsy is consistent with CRi or better response, but still a minimal percentage of peripheral blasts is detected, the response assessment can be postponed up to 2 weeks and will be based on repeated peripheral blood results and last bone marrow aspiration results.

12.1. Efficacy analysis

The Overall Survival (OS) is calculated as:

- In case of all-cause death:
 $OS = date\ of\ death - date\ of\ first\ study\ drug\ administration + 1;$
- In case of censored information not for drop-out:
 $OS = date\ of\ end\ of\ observation\ period\ (i.e.\ study\ end / end\ of\ survival\ follow-up) - date\ of\ first\ study\ drug\ administration + 1;$
- In case of censored information for drop-out:
 $OS = last\ date\ known\ alive - date\ of\ first\ study\ drug\ administration + 1.$

The Relapse Free Survival (RFS) is calculated as:

- In case of relapse or all-cause death:
 $RFS = date\ of\ relapse\ or\ death\ (whichever\ comes\ first) - date\ of\ first\ CR,\ CRi,\ CRh\ or\ CR_{MRD-} + 1;$
- In case of censored information:
 $RFS = date\ of\ last\ relapse-free\ disease\ assessment - date\ of\ first\ CR,\ CRi,\ CRh\ or\ CR_{MRD-} + 1.$

The Event Free Survival (EFS) is calculated as:

- In case of relapse, treatment failure or all-cause death:
 $EFS = date\ of\ relapse,\ disease\ progression,\ treatment\ failure\ (failure\ to\ achieve\ CR/CRh/CRi/CR_{MRD-}\ after\ at\ least\ five\ cycles\ of\ treatment)\ or\ death\ (whichever\ comes\ first) - date\ of\ first\ study\ drug\ administration + 1;$
- In case of censored information:
 $EFS = date\ of\ last\ relapse-free/treatment-failure-free/progression-free\ disease\ assessment - date\ of\ first\ study\ drug\ administration + 1.$

The Duration of Response (DoR) is calculated as:

- In case of relapse, progressive disease or death due to progressive disease:
 $DoR = date\ of\ relapse\ of\ any\ type/progressive\ disease/death\ due\ to\ progressive\ disease - date\ of\ first\ CR,\ CRi,\ CRh,\ CR_{MRD-},\ MLFS\ or\ PR + 1;$
- In case of censored information:
 $DoR = date\ of\ last\ relapse-free\ disease\ assessment - date\ of\ first\ CR,\ CRi,\ CRh,\ CR_{MRD-},\ MLFS\ or\ PR + 1.$

No formal statistical analysis will be performed on anti-leukemic parameters.

Anti-leukemic activity data will be collected throughout Part 1 and Part 2 and will be summarized by cohort, by dose and overall.

Measures of anti-leukemic activity will be computed on both safety and efficacy populations and they will include:

- Changes (absolute and %) in pre- and post-treatment levels of leukemic blasts in the peripheral blood and/or bone marrow;
- Number and percentages of patients who reported as best overall response one of the following: CRM RD-, CR, CRh, CRi, MLFS, PR, SD, PD;
- Duration of response (DoR);
- Relapse-free survival (RFS);
- Event-free survival (EFS);
- Overall Survival (OS);
- Transfusion conversion rate;
- Transfusion maintenance rate;
- HSCT rate.

OS, RFS, EFS rates at specific timepoints (e.g. 6, 12 months) may also be performed with exploratory intent.

Transfusion conversion rate, transfusion maintenance rate and HSCT rate will be evaluated only in the IDH-mutants cohort.

Where possible disease assessment will be evaluated according to the response criteria in AML6 (Appendix D of Study Protocol). Efficacy analyses will be performed through descriptive statistics.

